### 9.3.3 Evaluation of Pharmacodynamic Parameters

The PD markers, circulating cytokine levels, will be summarized using descriptive statistics: N, mean, SD, min, max, median, coefficient of variation as a percent (CV %), and GM by dose level.

Any p-values that will be calculated according to the analysis plan will be interpreted in view of the exploratory nature of the study.

### 9.3.4 Evaluation of Immunogenicity

The proportion of samples positive for ADA and the proportion of subjects with any sample positive for ADA will be summarized by dose using descriptive statistics. The PK parameters of all subjects and subjects with no sample positive for ADA will be summarized to assess whether ADA has an impact on PK.

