	
endpoints in CDx+ subjects will be summarized and compared between PRA023 and placebo groups in FAS for CDx+, while the treatment difference will be estimated with 95% CI. Additional efficacy analysis will be detailed in SAP.
 
Interim Efficacy Analysis: An interim analysis will be carried out when approximately 80% of subjects (approximately 96 subjects) in Cohort 1 have reached Week 12 or early terminated from the study. The DMC will review the unblinded efficacy and safety data and recommend whether to continue enrollment into Cohort 2. Decision rules to continue Cohort 2 are to be determined according to the futility bounds of group sequential design of a sample size of 40 per arm with one interim analysis at the information fraction of 45%. Because the exact bounds will be calculated using the actual number of subjects with CDx+ included in the interim analysis, the final decision rules, along with sensitivity analysis, will be specified in the DMC SAP, prior to the interim analysis.
 
Adverse Events: AEs will be coded using the most current version of Medical Dictionary for Regulatory Activities (MedDRA®). A by-subject AE data listing, including verbatim term, preferred term (PT), system organ class (SOC), treatment, severity, seriousness criteria, relationship to drug, and action taken, will be provided. The number of subjects experiencing treatment-emergent adverse events (TEAEs) and number of TEAEs will be summarized by treatment using frequency counts for Safety analysis set. Medical History, chest x-ray, electrocardiogram (ECG), and physical examination will be listed by subject. Changes in ECGs and physical examinations will be described in the text of the final report.
 
Concomitant Medications: Concomitant medications will be coded using the most current World Health Organization (WHO) drug dictionary and listed by treatment.
 
Pharmacokinetics: Summary statistics of PRA023 concentrations and anti-drug antibody (ADA) by visit and by CDx+ and CDx-.

--	--

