### **Prohibited Therapies and/or Medications**

- 26. Failed (no response, insufficient response, loss of response, and/or intolerance) > 3 classes (anti-TNF, anti-integrin, anti-IL12/23, JAK inhibitor, S1PR modulator) **or** > 4 individual biologic/biologic-like therapies.
- 27. Any marketed biologic or biologic-like within 2 weeks for JAK inhibitors (e.g., tofacitinib, upadacitinib or filgotinib), 8 weeks for anti-TNF agents, 10 weeks for S1PR modulators (e.g., ozanimod), and 12 weeks for vedolizumab and anti-IL-12/23 (e.g., ustekinumab) prior to randomization **or** if drug level per therapeutic dose monitoring is greater than lower limit of detection.
- 28. Any biologic immunomodulators not covered in exclusion criterion 27, used for UC or other conditions within 8 weeks or 5 half-lives, whichever is longer, prior to randomization **or** if drug level per therapeutic dose monitoring is greater than lower limit of detection.
- 29. Rituximab within 1 year prior to randomization.
- 30. Parenteral corticosteroids within 4 weeks or rectal administration of corticosteroids within 2 weeks prior to randomization.
- 31. Rectal administration of 5-ASA within 2 weeks prior to randomization.
- 32. Tacrolimus, methotrexate, cyclosporine, mycophenolate mofetil (CellCept®), immunoadsorption columns (such as ProSORBA columns), d-penicillamine, leflunomide, thalidomide, fish-oil preparations, probiotics, fecal transplantation, non-steroidal anti-inflammatory agents (NSAIDs), aspirin > 81 mg/day within 2 weeks prior to randomization.
- 33. Other investigational chemical agent within 30 days or other investigational biologic agent within 8 weeks or 5 half-lives (whichever is longer) of randomization.
- 34. Prior exposure to PRA023.

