Pharmacokinetic Sub-Study (Optional)	X a				X a			a. In addition to the PK samples obtained in all subjects, PK sub-study subjects will have the following samples obtained: Week 0/Day 1 and Week 10: 4 days (96±5 hours) and 1 week (168±5 hours) after completion of infusion. Refer to Section 6.6.1 for additional details.
Immunogenicity	X	X	X	X		X	X	To be taken pre-infusion.
Biomarkers								
Biomarkers	X	X	X	X	X	X	X	Serum at all visits; additional whole blood at Weeks 0, 6, and 12
Soluble TL1A	X	X	X	X	X	X	X	
hsCRP	X	X	X	X	X	X	X	
Fecal Calprotectin	X			X		X	X	
Infusion	X	X	X	X	X			Include date, start and stop time, volume infused, and length of the IV infusion. Observation period at Week 0/Day 1 and Week 2 will be 1 hour (2 hours for subjects in Czech Republic); 30 minutes for all subsequent infusions thereafter.

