## 6.7 Immunogenicity (Anti-Drug Antibody)

Antibodies to PRA023 will be evaluated in blood samples collected from all subjects at time points specified in the protocol (see Section 6.1.1). These samples will be tested by the Sponsor or Sponsor's designee. Instructions for the handling of ADA samples will be provided in the Laboratory Manual.

Blood samples will be screened for antibodies binding to PRA023 and the titer of confirmed positive samples will be reported. Other analyses may be performed to verify the stability of antibodies to PRA023 and/or further characterize the immunogenicity of PRA023.

The detection and characterization of antibodies to PRA023 will be performed using a validated assay method by or under the supervision of the Sponsor. All samples collected for detection of antibodies to PRA023 will also be evaluated for PRA023 serum concentration to enable interpretation of the antibody data. If confirmed positive, antibodies may be further characterized and/or evaluated for their ability to neutralize the activity of PRA023.

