### 8.3 Evaluation of Safety Variables

Data will be summarized with respect to safety observations. Monitoring of AEs, physical examinations, vital signs, ECGs, safety and tolerability monitoring evaluations, clinical laboratory evaluations, and special procedures are detailed in [Section 6.3](#).

All available safety data for all randomized subjects who receive at least one dose of PRA023 will be included in the safety analysis, which will be primarily descriptive.

The safety variables will be:

- Hematology, chemistry, coagulation, and urinalysis
- Vital signs
- ECG parameters

- Physical examination
- AEs and SAEs
  - AEs of special interest: infections, acute infusion reaction (within 1 hour of completion of infusion), and peri-infusion reaction (within 24 hours of completion of infusion)
  - AEs in subjects who are ADA positive

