#### **9.3.7.1 Adverse Events and Adverse Events of Special Interest**

All AEs will be coded using most current version of Medical Dictionary for Regulatory Activities (MedDRA). All reported adverse events will be assigned to the SOC and PT according to MedDRA. The number and percentage of subjects reporting adverse events (all, serious, related) will be tabulated by overall and treatment. AEs will be summarized by SOC and PT. AEs will also be summarized by relationship to the study drug, seriousness and severity.

A treatment-emergent AE (TEAE) will be defined as an AE that began or worsened on or after the first treatment dose. AEs recorded prior to the first infusion of study treatment will be considered non-treatment-emergent.

All reported AEs (treatment-emergent or not) will be listed. Only TEAEs will be summarized.

AEs of special interest including infections, acute infusion reaction (within 1 hour of completion of infusion), and peri-infusion reaction (within 24 hours of completion of infusion) will be summarized based on a pre-specified MedDRA list.

AEs occurring in subjects who are considered immunogenicity positive will also be summarized.

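### The subject-level ADA proportion in Protocol Section 9.3.4 counts any positive sample, including those taken before any PRA023, so it mixes pre-existing reactivity with antibodies induced by the drug

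*Protocol*

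**What the plan says.** Protocol Section 9.3.4 summarizes ADA in two ways, as a proportion of samples and as a proportion of subjects. For subjects the rule is that "the proportion of subjects with any sample positive for ADA will be summarized by dose using descriptive statistics". The same section then sets up a PK comparison, quoted here without its last word: "The PK parameters of all subjects and subjects with no sample positive for ADA will be summarized to assess whether ADA has an impact on". Neither rule is limited to samples taken after exposure.

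The induction schedule (Section 6.1.1, Table 2) has an immunogenicity row that begins at Week 0/Day 1, with the note "To be taken pre-infusion". Section 4.2.1.2 excludes "Prior exposure to PRA023".

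On the assay, Section 6.7 says "Blood samples will be screened for antibodies binding to PRA023 and the titer of confirmed positive samples will be reported". It gives no rule for baseline status or for a rise in titer.

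Three other places use ADA results:
- The Synopsis, under Pharmacokinetics, plans "Summary statistics of PRA023 concentrations and anti-drug antibody (ADA) by visit and by CDx+ and CDx"-negative status.
- Section 8.3 lists "AEs in subjects who are ADA positive" among the safety variables.
- Section 9.3.7.1 says "AEs occurring in subjects who are considered immunogenicity positive will also be summarized".

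Neither AE passage says what makes a subject positive.

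**The concern.** An ADA incidence is normally read as the share of subjects who form antibodies because of the drug. A rule that accepts any positive sample also counts subjects who were reactive before they received any. The two groups have different causes and may differ in their consequences for exposure and safety, and a single pooled proportion cannot tell them apart.

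The crossover adds to this. Subjects who complete induction may enter the extension, where everyone receives PRA023 (Section 4.1). For a placebo subject, all induction samples come before the first PRA023 dose, and the rule does not set them aside.

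The protocol makes this kind of distinction for adverse events: Section 9.3.7.1 defines treatment emergence relative to the first dose and summarizes only treatment-emergent events. Nothing in the available text does the same for ADA. What is at stake is the ADA rate itself and the reading of the PK summary built on the same rule.

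**Working it through.** The plan states no ADA rate, so there is no figure to reproduce. The check has two parts.

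**Reading the rule against the schedule**
1. Any positive sample makes the subject positive (Section 9.3.4).
2. The first sample is taken before the first infusion (Table 2).
3. No subject has had PRA023 before (Section 4.2.1.2), so a Week 0 positive reflects pre-existing reactivity or assay background.
4. The subject is counted all the same.

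**Size, under assumed rates**

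Let b be the share of subjects positive before any PRA023 and t the treatment-emergent rate. Neither is in the documents. The ranges used are b = 1% to 10% and t = 5% to 20%, with the two events taken as independent.

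- Rate under the rule: b + (1-b)t
- Excess over t: b(1-t)
- Share of counted subjects who were already positive: b / [b + (1-b)t]

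Example with b = 5% and t = 10%: 0.05 + 0.95 × 0.10 = 0.145. The excess is 0.05 × 0.90 = 4.5 points, and the share already positive is 0.05/0.145 = 34.5%. In an arm of 60 (Section 8.2) that is 60 × 0.145 = 8.7 expected positives against 60 × 0.10 = 6.0.

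| b | t | Rate under the rule | Excess (points) | Share already positive |
|---|---|---|---|---|
| 1% | 5% | 5.95% | 0.95 | 16.8% |
| 1% | 10% | 10.9% | 0.90 | 9.2% |
| 1% | 20% | 20.8% | 0.80 | 4.8% |
| 5% | 5% | 9.75% | 4.75 | 51.3% |
| 5% | 10% | 14.5% | 4.50 | 34.5% |
| 5% | 20% | 24.0% | 4.00 | 20.8% |
| 10% | 5% | 14.5% | 9.50 | 69.0% |
| 10% | 10% | 19.0% | 9.00 | 52.6% |
| 10% | 20% | 28.0% | 8.00 | 35.7% |

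In relative terms the excess is b(1-t)/t. It runs from 0.01 × 0.80/0.20 = 4% to 0.10 × 0.95/0.05 = 190%; the upper end needs background reactivity twice as common as induced ADA. At b = 0 the excess is zero.

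The chance of at least one baseline positive among 60 subjects is 1-(1-b)^60: 45% at b = 1%, 95% at 5% and 99.8% at 10%.

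**The other statistic can move the opposite way.** Pre-dose samples also enter the denominator of the proportion of samples. With no baseline positives and, as an assumption, five samples per subject of which one is pre-dose, that proportion is 4/5 = 0.80 of its post-dose value.

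**What the by-visit summary can show.** Suppose 3 of 60 subjects are positive at Week 0 (b = 5%) and 3 of 60 at Week 12. These could be the same three, with no induced ADA, or a different three, with 3/57 = 5.3% induced. Proportions by visit do not separate these cases.

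**The case against.** The strongest reply is that the plan as a whole does not hide pre-existing antibodies. The by-visit summary in the Synopsis would show Week 0 positivity, Section 6.7 provides titers for confirmed positives, and all samples are kept, so the split can still be made at reporting. That stands, and it limits the point to the pooled subject-level proportion. The by-visit display is planned by CDx status, with no mention of treatment arm, and as shown above it does not give incidence.

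A reader might infer more than the documents support:
- **That the AE tables misclassify subjects.** Sections 8.3 and 9.3.7.1 leave their positive category undefined and do not adopt the rule in 9.3.4. The fault there is a missing definition.
- **That placebo has no row.** A tabulation by dose could include placebo as a level; the text does not say.
- **That a placebo subject's induction positive is carried into a PRA023 row after crossover.** No passage says so. The rule only fails to set such samples aside.
- **That the PK grouping is wrong.** Pre-existing antibodies may also affect PK, so a never-positive group is a sound reference. Classifying by treatment-emergent status alone would move baseline-positive subjects without a titer rise into that reference and blur the contrast.

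SAP V01 was also unavailable. Protocol Section 9 defers detail to the SAP, and the addendum deals only with multiplicity and the CDx+ analyses. SAP V01 may already define treatment-emergent ADA. Even so, protocol version 5.0 (14 June 2023), which postdates SAP V01 (10 August 2022), still carries the any-sample rule, so the two would need aligning.

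Finally, ADA is not among the listed objectives or endpoints, its summary is descriptive, and no efficacy test, alpha allocation or stated Cohort 2 decision rule uses it.

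**Conclusion.** The point holds for the subject-level ADA proportion in Section 9.3.4. As written, it includes samples taken before any PRA023 and so mixes pre-existing with induced reactivity. The excess is b(1-t). Over the assumed ranges this is 0.8 to 9.5 points, and it is zero if nobody is positive before exposure. The direction for this proportion is certain whenever b is above zero; the size is unknown, because the documents give no background rate. The formula assumes that pre-existing and treatment-emergent positivity are independent.

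It would go too far to conclude that the plan presents pre-existing antibodies throughout as immunogenicity of PRA023, or that the AE summaries are already wrong. The first overlooks the by-visit summary and the second rests on a definition that the text does not give. The change is worth making because the rule is explicit, a better one is cheap, and the data for it are already collected. It has no bearing on the efficacy conclusions.

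**What to change.** Unless SAP V01 already does so, amend Section 9.3.4 and carry the same definitions into the SAP:

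1. **Baseline:** the last sample before the first PRA023 dose. This is Week 0 for the PRA023 arm and Week 12 for placebo subjects who enter the extension. As extracted, Tables 3 and 4 show no immunogenicity sample at Week 14; column alignment should be checked.
2. **Treatment-emergent ADA:** baseline negative and positive after the first PRA023 dose, or baseline positive with a titer rise of a size fixed in advance. State the denominator as subjects with an evaluable baseline and at least one later sample.
3. **Background:** report baseline-positive prevalence separately, and show placebo through Week 12 as its own level.
4. **PK:** keep the never-positive group as the reference, and show pre-existing and treatment-emergent ADA as separate categories.
5. **AEs:** state in Sections 8.3 and 9.3.7.1 that the same categories apply.

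The cost is one set of definitions and a little more tabulation, with few subjects in some categories. No sample or assay is added, since titers are already reported under Section 6.7.

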#### 6.6 Pharmacokinetics

Blood samples for pharmacokinetics are to be drawn at the time points specified in the protocol (see [Section 6.1.1](#)). Blood samples for PK analysis of PRA023 concentrations will be collected from each subject and will be analyzed using a validated assay method by or under the supervision of the Sponsor. The PK blood samples will be obtained according to the study flowchart. The actual date and time (24-hour clock time) of each sample will be recorded. Instructions for the handling of the PK samples will be provided in the Laboratory Manual.

Changes in the timing or addition of time points for any planned study assessments must be documented and approved by the relevant study team member and then archived in the Sponsor and study center study files, but will not constitute a protocol amendment. The IRB/IEC will be informed of any safety issues that require alteration of the safety monitoring scheme or amendment of the ICF. PK analysis will be performed as outlined in the PK section of the Statistical Analysis Plan (SAP).

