### 8.2 Justification of Sample Size

The study is planned to randomize up to approximately 170 subjects, approximately 120 in Cohort 1 and up to 50 in Cohort 2. A sample size of 60 per arm in Cohort 1 will enable a statistical power of > 80% for the primary endpoint at 1-sided significance level of 0.025 using Cochran-Mantel-Haenszel (CMH), assuming clinical remission rate of 5% for placebo and 24% for PRA023. Additionally, the sample size will confer > 80% power to achieve statistical significance for the 1st secondary endpoint of endoscopic improvement with an overall 1-sided alpha level of 0.025, assuming the endoscopic improvement rates are 15% and 38% for placebo and PRA023 groups, respectively.

Additionally, for analyses of the CDx+ population (combining CDx+ subjects from Cohort 1 and Cohort 2), a sample size of 40 per arm will provide a statistical power of  $\geq 80\%$  at a 1-sided alpha level of 0.025, according to a group sequential design with a non-binding futility interim analysis when approximately 18 subjects are anticipated per arm reach Week 12, assuming clinical remission rate of 5% for placebo and 31% for PRA023.

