### **9.3.6 Evaluation of Pharmacokinetic Parameters**

PK parameters will be computed, as appropriate, from the individual serum concentrations using a non-compartmental approach. All PK parameters will be summarized using descriptive statistics: N, mean, SD, min, max, median, CV %, and GM and GM CV%. Serum concentrations of PRA023 will be summarized.

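### Section 9.3.4 assesses the effect of ADA on PK with two overlapping groups, so the displayed difference is only the ADA-positive fraction of the real one

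*Protocol*

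**What the plan says.** Protocol section 9.3.4 plans two things for immunogenicity. The first is incidence: alongside the share of positive samples, "the proportion of subjects with any sample positive for ADA will be summarized by dose using descriptive statistics". The second is the link to exposure: "PK parameters of all subjects and subjects with no sample positive for ADA will be summarized to assess whether ADA has an impact on PK". That sentence states its own purpose, so this pair of summaries is the planned means of judging the ADA effect.

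Section 9.3.6 sets the statistics: "All PK parameters will be summarized using descriptive statistics: N, mean, SD, min, max, median, CV %, and GM and GM CV"%. It does not split by ADA status. The Pharmacokinetics line of the synopsis splits by visit and CDx status only. The SAP addendum does not mention ADA.

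The data for a direct comparison will exist. Section 6.7 states: "All samples collected for detection of antibodies to PRA023 will also be evaluated for PRA023 serum concentration to enable interpretation of the antibody data". It also has titers reported for confirmed positives.

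More PK detail is deferred. Section 6.6 says "PK analysis will be performed as outlined in the PK section of the Statistical Analysis Plan (SAP"). That section would be in SAP V01 (10 August 2022), which is not among the documents reviewed. The addendum only replaces the multiplicity section of V01 and adds the CDx+ analyses.

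**The concern.** The group with no ADA-positive sample is a subset of all subjects. Setting a whole beside a part of itself shows only what the remaining part contributes to the whole. If few subjects are ADA-positive, the two columns will be close whatever happens to exposure in those few. A reader who takes the sentence at its word could conclude that ADA has little effect on PK when the table could not have displayed a large one.

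What is at stake is the interpretation of an exploratory PK result. Neither the protocol nor the addendum plans a PK summary for ADA-positive subjects that would correct the impression.

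**Working it through.** The plan gives no figure for this analysis, so there is nothing of its own to reproduce.

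**Inputs**
- The two groups: all subjects, and subjects with no ADA-positive sample (Protocol 9.3.4).
- The statistics shown: N, mean, geometric mean, median, range and spread (9.3.6).
- Illustrative number on PRA023: "A sample size of 60 per arm in Cohort 1" (8.2), so 60.
- p, the ADA-positive fraction: not in the documents. Assumed 5–30%.
- r, exposure in ADA-positive divided by exposure in ADA-negative subjects: not in the documents. Assumed 0.7 to 0.3, a loss of 30–70%.

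**Identities (exact)**
- Arithmetic: mean(all) = p × mean(pos) + (1 − p) × mean(neg). Hence mean(all) − mean(neg) = p × [mean(pos) − mean(neg)], and mean(all)/mean(neg) = 1 − p(1 − r).
- Geometric: log GM(all) = p × log GM(pos) + (1 − p) × log GM(neg). Hence GM(all)/GM(neg) = r^p, with r now the ratio of geometric means.

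**Central illustration, p = 10%, r = 0.5**
- Arithmetic: 1 − 0.10 × 0.5 = 0.950, a 5% difference.
- Geometric: 0.5^0.10 = 0.933, a 7% difference (6.7% before rounding).
- Disjoint groups would show the full 50%.

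**Range: displayed reduction, arithmetic / geometric**

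| p | true loss 30% | true loss 50% | true loss 70% |
|---|---|---|---|
| 5% | 1.5% / 1.8% | 2.5% / 3.4% | 3.5% / 5.8% |
| 10% | 3.0% / 3.5% | 5.0% / 6.7% | 7.0% / 11.3% |
| 20% | 6.0% / 6.9% | 10.0% / 12.9% | 14.0% / 21.4% |
| 30% | 9.0% / 10.1% | 15.0% / 18.8% | 21.0% / 30.3% |

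**How far it can be undone.** With 60 subjects, 54 of them ADA-negative, suppose mean(neg) = 100 and mean(all) = 95. Then mean(pos) = (60 × 95 − 54 × 100)/6 = (5700 − 5400)/6 = 50. The same subtraction on logs recovers the geometric mean. It does not recover a median or a range.

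**How easily it is missed.** The plan specifies no test; this only gauges the visual impression. Assume a between-subject CV of 40%, so the log-scale SD is √ln(1 + 0.4²) = 0.385. Take 6 positive and 54 negative subjects and r = 0.5.
- Disjoint groups: z = 0.693 / [0.385 × √(1/6 + 1/54)] = 4.18.
- Overlapping summaries read as if independent: z = (0.10 × 0.693) / [0.385 × √(1/60 + 1/54)] = 0.96.
- Overlapping summaries with the overlap allowed for: the difference and its standard error both shrink by p, so z = 4.18 again.

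The data keep the information. The side-by-side display does not show it.

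**The case against.** The strongest reply is that little is lost. Section 9.3.4 says the groups will be summarized; it sets no test, threshold or decision rule. PK is an exploratory objective (section 2.3). The ADA-positive mean and geometric mean follow by subtraction from the planned output, and section 9 promises individual data listings. SAP V01 may already tabulate ADA-positive subjects. All of this stands. It makes the point a modest improvement to a descriptive display, and it makes the remedy conditional on SAP V01. It does not rescue the sentence, which names a purpose that the named pair of summaries serves poorly.

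It is also fair to say that the size is assumed. At the top of the range the gap is 21% or 30%, which a reader would notice. The dilution is severe when p is small and moderate when it is not.

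Three stronger readings are tempting, and the documents do not support them.
- A reader might infer that the safety summary suffers too. It does not: section 9.3.7.1 says "AEs occurring in subjects who are considered immunogenicity positive will also be summarized", which isolates the ADA-positive group without using the PK summaries.
- A reader might infer that the comparison of the 100 mg and 250 mg maintenance regimens, or an efficacy conclusion, depends on this summary. Nothing in the documents makes it so.
- A reader might take the synopsis line on concentrations and ADA as a second instance. It neither repeats the overlap nor rules out a split by ADA status.

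**Conclusion.** The point holds for the protocol text. Read side by side as planned, the two summaries understate any ADA effect on exposure, showing p times the difference in means, or r^p as a ratio of geometric means. At an assumed p of 10% and a true loss of 50%, that is 5% or 7%; over p of 5–30% and losses of 30–70%, it is 1.5–21% arithmetic or about 2–30% geometric. The identities are exact; p and the loss are assumptions, because the documents give neither.

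A reader might go further and say the analysis is bound to conclude that ADA has no impact, or that an effect would be irretrievably hidden. Neither follows. There is no decision rule, and means and geometric means can be back-calculated. The harm is to interpretation, not to an error rate. The finding covers the protocol and the SAP addendum only, since the PK section of SAP V01 could not be checked.

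**What to change.** Replace the sentence in section 9.3.4 with:

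> *PRA023 concentrations and PK parameters will be summarized separately for ADA-positive and ADA-negative subjects among those who received PRA023, by regimen received, with n and spread shown.*

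Keep the all-subjects column for reference, and align the text with the PK section of SAP V01. If V01 already has this split, only the protocol sentence needs to be brought into line. Splits by titer, or before and after the first positive sample, are optional where numbers allow.

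The cost is a wording change and a regrouped table; no new samples are needed, because every ADA sample is also assayed for drug. The downside is a possibly small ADA-positive group: at an assumed 10%, 6 of the 60 Cohort 1 subjects on PRA023. Non-compartmental parameters may rest on fewer still, because the extra post-dose samples come only from the optional PK sub-study (section 6.6.1 and Table 2). That is the reason to include concentrations, show n and spread, and leave the finer splits optional.
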